- Alcohol or drug abuse
- Received an analgesic within the last four hours
- History of congestive heart failure
- History of aortic or brain aneurysm
- Active Chest Pain
- Porphyria
- Active methadone treatment
- Pregnant or breastfeeding
- Signs of respiratory, hemodynamic, or neurologic compromise
 - Systolic blood pressure < 90 mmHg or > 180 mmHg
 - Heart rate < 50 beats per minute or > 150 beats per minute
 - Respiratory rate < 10 breaths per minute or > 30 breaths per minute
 - Glasgow Coma Score < 15
- Previously received ketamine ≤ 0.3 mg/kg IV for acute pain in the emergency department

VI. Recruitment Procedures

This is a single-center, prospective, randomized, double-blind, active controlled trial that will identify patients in the emergency department with acute pain who meet the eligibility criteria from January 2019 through January 2021 to achieve a sample of at least 180 patients.

VII. Definitions

Adequate pain relief:

- A score decrease on the Numerical Rating Scale (NRS) by ≥ 3 points

Moderate pain:

- A NRS score of 4-7 out of 10 per hospital policy

Severe pain:

- A NRS score of 8-10 out of 10 per hospital policy

Rescue analgesia:

- Any IV analgesic to be determined by the treating provider

Opioid tolerant:²⁵

- Patients receiving, for one week or longer, at least 60 mg oral morphine/day, 25 mcg transdermal fentanyl/hour, 30 mg oral oxycodone/day, 8 mg oral hydromorphone/day, 25 mg oral oxymorphone/day, or an equianalgesic dose of another opioid

VIII. Methodology

This is a single-center, prospective, randomized, double-blind, active-controlled trial. Patients who meet inclusion criteria and none of the exclusion criteria will be enrolled from January 2019 to January 2021 to achieve a goal sample size of 180 patients. Data such as demographics, self-reported pain score, adverse drug events, vital signs, and need for rescue analgesia within two hours of ketamine administration will be reported. Outcomes will include pain score reduction, incidence and severity of adverse drug events, adequate pain relief, and need for rescue analgesia within two hours of ketamine administration. All data will be entered in a password protected data sheet for proper analysis. No patient identifying data will be recorded.

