- Treating resident or attending will notify the ED pharmacist that a patient has been enrolled in the trial
- ED pharmacist will notify the IV room and place the study drug order
- Either the ED pharmacist or a pharmacy supervisor will randomize the subject based on the predetermined randomization list
- Study drug will be prepared as 0.1 mg/kg, 0.2 mg/kg, or 0.3 mg/kg IV dose in a 100 mL solution of dextrose 5% or sodium chloride 0.9%
- ED pharmacist will promptly deliver the study drug to the ED
- Baseline vital signs will be assessed prior to starting the study drug infusion
- Study drug will be administered via IV infusion over 20 minutes
- Treating resident or attending will reassess the patient at 15 minutes from the end of infusion, at 30 minutes from the end of infusion, and then every 30 minutes for up to 120 minutes or until discharge, whichever is sooner

IX. Statistical Considerations

Randomization

The study participants will be randomly assigned into one of the three dose groups in the ratios of 1:1:1. Block randomization will be used to balance the sample size in each group.

Primary Outcome

The primary outcome is the numerical rating scale (NRS) pain score reduction from baseline to 120 minutes after the injection. The null hypothesis is that there is no difference among those three doses with respect to the mean score reduction.

Describing Data

The continuous variables (such as age of participant at the time of study) will be summarized using mean, median, standard deviation, interquartile range, range, minimum and maximum. The discrete variables (such as sex) will be summarized using frequency and percentage.

Exploring Differences

The two-sample Student's t-test will be used to compare the continuous variables between groups. If the normality assumption is violated, the Wilcoxon rank sum test will be used. The Shapiro-Wilk test will be used to evaluate the normality. The one-way analysis of variance (ANOVA) will be used to compare the continuous variables among groups. The Bartlett test will be used to evaluate the homogeneity of variances. The Tukey Honest Significant Differences test will be used to perform the multiple comparisons. If the normality assumption or homogeneity of variances assumption is violated, the Kruskal-Wallis one-way ANOVA by ranks will be used. The Dunn test will be used to perform the multiple comparisons.

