The chi-square test will be used to compare the categorical variables between or among groups. If the expected frequency in any cell of the contingency table is less than 5, the Fisher's exact test will be used.

The 95% confidence interval on the variables of interest will be calculated. The 2-sided p value will be reported for each test. A p value of 0.05 or less will be considered an indication of statistical significance.

Exploring Associations

When necessary, graphical techniques will be used to display the statistical results. The scatter plots will be used to explore the associations between two continuous variables, and the Pearson's correlation coefficient or Spearman's correlation coefficient will be calculated to assess the potential linear association between two continuous variables based on the normality of data. Due to the nature of exploratory study, the regression models will be explored if there is any significant difference identified from the results of previously described statistical testing.

Conducting Analysis

Statistical analysis will be performed using the R language (R Core Team [2018]. R: A language and environment for statistical computing. R Foundation for Statistical Computing, Vienna, Austria. URL <https://www.R-project.org/>) or SAS software, Version 9.4 for Windows (SAS Institute Inc., Cary NC, USA. URL <http://www.SAS.com>).

Power and Sample Size

There is no existing study from which the reductions in NRS score were compared among the three doses of interest. Therefore, this study is considered an exploratory study to explore the possible reduction in NRS score as well as the chance of developing adverse events under a randomized clinical trial setting. With the consideration of both efficacy and safety, we propose including 60 subjects in each group in order to get more information regarding the safety for planning on a larger scale study.

After finishing the exploratory study, based on the mean reduction in each group, if we can find the potential clinical benefits are important, we will then estimate the necessary sample size in order to show the statistical significance. For example, if we can find the potential of clinical importance in primary outcome (such as a mean difference of 1.25 between consecutive doses with the standard deviation of 3.4), in order to show that the reductions are different among doses, with the significant level of 0.05 and power of 80%, if we want to have equal number of

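### The tests listed for the 120-minute NRS reduction use one time point and no baseline covariate, and no rule covers patients discharged before 120 minutes; a repeated-measures primary analysis would use scores already on the form

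*Combined protocol and SAP*

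**What the plan says.** Section IX, Primary Outcome: "The primary outcome is the numerical rating scale (NRS) pain score reduction from baseline to 120 minutes after the injection". It continues: "The null hypothesis is that there is no difference among those three doses with respect to the mean score reduction".

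No sentence assigns a test to this outcome. Under Exploring Differences, the three-group methods for continuous variables in general are: "The one-way analysis of variance (ANOVA) will be used to compare the continuous variables among groups", followed by Tukey, and "If the normality assumption or homogeneity of variances assumption is violated, the Kruskal-Wallis one-way ANOVA by ranks will be used", followed by Dunn. The only opening for an adjusted analysis is under Exploring Associations, where "the regression models will be explored if there is any significant difference identified from the results of previously described statistical testing". That sentence names no covariates or time points and depends on an earlier p-value.

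Section VIII, in both its narrative and its Procedure list, ends assessment at discharge if that comes before 120 minutes. The Appendix A form holds a pre-randomisation pain score, pain columns at 15, 30, 60, 90 and 120 minutes, and a rescue Y/N entry for each column. Its vital-signs line allows for discharge; its pain row does not.

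The plan gives no analysis population, no rule for a missing 120-minute score, and no rule for scores after rescue.

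Under Power and Sample Size, the decision on a larger study is to be taken "based on the mean reduction in each group, if we can find the potential clinical benefits are important".

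**The concern.** A patient discharged before 120 minutes has no value for a single-time test unless someone supplies one. The plan does not say whether such patients are dropped, carried forward or modelled, so the choice could be made after the data are seen. If patients with better relief tend to leave sooner, dropping them pulls every arm mean down, and carrying their last score forward pushes it up. The arm means feed the decision on the next study. If discharge practice also differs by dose, the dose comparison itself is affected. Meanwhile the earlier scores, which carry much of the missing information, are collected but have no role in the listed tests.

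**Working it through.** **Inputs from the plan.** 60 patients per arm; an illustrative step of 1.25 points between consecutive doses and SD 3.4 (Section IX, Power and Sample Size); a 3-point decrease as adequate relief (Section VII).

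**The plan's own figure.** The illustrative 157 per group for a later study reproduces as a two-sided two-sample t-test at alpha 0.05/3 with 80% power (156.35, rounded up). The plan does not state the division by 3. The figure contains no allowance for missing scores.

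**Assumptions not in the documents.** True mean reductions 2, 3.25 and 4.5 at both 60 and 120 minutes; correlation rho = 0.7 between those times; a proportion p of patients with at least 3 points of relief at 60 minutes leaves then, with p = 20% or 50%.

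**Formulas (normal, unbounded scores).** With a = (3 - mu)/3.4, phi the normal density and Q the upper tail:
- missing fraction = p x Q(a)
- complete-case mean = mu - rho x 3.4 x p x phi(a) / (1 - p x Q(a))
- carried-forward mean = mu + (1 - rho) x 3.4 x p x phi(a)

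Example, mu = 2 and p = 0.5: a = 0.294, phi = 0.382, Q = 0.384. Missing = 0.192. Complete-case = 2 - 0.7 x 3.4 x 0.5 x 0.382/0.808 = 1.44. Carried forward = 2 + 0.3 x 3.4 x 0.5 x 0.382 = 2.20 (2.195 before rounding).

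| True mean | p | Missing | Complete-case | Carried forward |
|---|---|---|---|---|
| 2.00 | 20% | 7.7% | 1.80 | 2.08 |
| 3.25 | 20% | 10.6% | 3.04 | 3.33 |
| 4.50 | 20% | 13.4% | 4.30 | 4.57 |
| 2.00 | 50% | 19.2% | 1.44 | 2.20 |
| 3.25 | 50% | 26.5% | 2.61 | 3.45 |
| 4.50 | 50% | 33.5% | 3.85 | 4.69 |

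Modelling the earlier score returns the true means. A simulation with integer 0-10 scores (baseline mean 7.5, SD 1.8, limited to 4-10) agrees. Against true means of 2.00, 3.24 and 4.51, complete-case gives 1.79, 3.04, 4.35 (20%) and 1.41, 2.60, 3.95 (50%). Carrying forward gives 2.10, 3.34, 4.59 and 2.24, 3.48, 4.71.

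**Sensitivity.** Over correlations 0.5-0.9 (unbounded scores) the complete-case shortfall is 0.14-0.84. If relief wanes by 1-2 points between 60 and 120 minutes, carrying forward is 0.2-1.0 too high.

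**Contrast, same rule in every arm.** High minus low, complete-case: 4.30 - 1.80 = 2.50 and 3.85 - 1.44 = 2.41, against a true 2.50. With 0-10 scores it stays at 2.47-2.55 under both rules.

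**Contrast, different rule by arm.** 20% leaving in the low arm and 50% in the high arm: 3.85 - 1.80 = 2.05 complete-case. Reversed: 4.30 - 1.44 = 2.86. Carried forward: 4.69 - 2.08 = 2.61 and 4.57 - 2.20 = 2.37. With earlier scores modelled: 2.50 in both. In a separate check with two arms of equal true mean 3.0 and 10% versus 30% leaving early, completers show a false difference of 0.30-0.53; modelling gives about 0.

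**Precision.** Standard error of the high-minus-low difference, 0-10 scores: complete-case ANOVA 0.65-0.73; with baseline 0.64-0.72; with earlier scores 0.62-0.65; with both 0.61-0.65.

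**Discharge depending on the unseen 120-minute relief.** Lowest arm, true 2.0: complete-case 1.71-1.19, model 1.88-1.67. The model removes (1.88 - 1.71)/(2.0 - 1.71) = 59% to (1.67 - 1.19)/(2.0 - 1.19) = 59% of the bias; with 0-10 scores about 55-57%.

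**Rescue.** If 30-70% of patients with under 3 points of relief at 60 minutes get rescue worth 2-3 points (assumed, no discharge), the contrast regardless of rescue moves from 2.5 to 2.33-1.91. That is a different question, not a bias, but the plan must say which question is primary.

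**The case against.** The strongest reply is that the plan is about differences between doses. Its objective, its null hypothesis and its example of clinical importance (1.25 between consecutive doses) are all contrasts, and a common discharge rule hardly moves them. From the 0-10 complete-case means, the steps are 3.04 - 1.79 = 1.25 and 4.35 - 3.04 = 1.31 at 20%, and 2.60 - 1.41 = 1.19 and 3.95 - 2.60 = 1.35 at 50%. This stands for a common rule. It does not cover discharge that differs by arm. That cannot be excluded: Appendix B describes emergence reactions as dose-related, and side effects could plausibly alter time to discharge.

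It also stands that the trial is declared exploratory, that discharge rates are pure assumption (the text permits early discharge but does not predict how much), and that baseline adjustment alone adds little precision with 0-10 scores.

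Four stronger readings are tempting, and the documents do not support them:
- That the listed tests are invalid. In a randomised trial with complete scores, an unadjusted single-time comparison is valid, and Tukey does control multiplicity.
- That the dose comparison is necessarily biased. That needs discharge to differ by arm, on which the documents are silent.
- That the middle arm reading 2.6 or 3.5 straddles a decision threshold. The 3-point figure, "A score decrease on the Numerical Rating Scale (NRS) by ≥ 3 points", is a per-patient definition and is nowhere applied to an arm mean.
- That the endpoint has no scheduled score. The Procedure list and the form both give one at 120 minutes. The wording differences are minor: the primary outcome counts from the injection, another outcome is the "need for rescue analgesia within two hours of ketamine administration", and the Procedure list counts from the end of a 20-minute infusion. From infusion start, 120 minutes is 120 - 20 = 100 minutes after its end. The narrative schedule in Section VIII, read literally, gives 15, 45, 75 and 105 minutes.

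**Conclusion.** The point holds, at moderate weight. The plan has a single-time primary outcome whose value can be absent by design, no rule for that case, and unused scores that would largely resolve it. The error in the arm means and in the contrast is as set out in the working; the contrast is at risk only where discharge differs by arm. All sizes rest on assumed discharge rates, an assumed correlation and, for the full correction, missingness that depends only on recorded scores. The precision gain is modest and comes mainly from the earlier scores. No claim is made about power, since the plan states none for 180 patients.

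**What to change.** 1. Make the primary analysis a mixed model for repeated measures on the five scheduled scores, with dose, time, dose-by-time, baseline NRS, baseline-by-time and unstructured covariance. Test the null with the joint 2-degree-of-freedom dose test at 120 minutes, give the three pairwise contrasts with a Tukey-type adjustment, and report the 120-minute arm means from the model. Keep ANOVA or Kruskal-Wallis as supportive.
2. State that the primary contrast uses scores regardless of rescue. Add one sensitivity analysis in the same model that sets aside scores after the first recorded rescue.
3. Add a simple not-at-random sensitivity analysis, for example a shift applied to missing 120-minute scores, because the model assumes missing at random and removes only part of the bias otherwise.
4. As a minor wording point, state one time origin for the 120-minute score and reconcile the Section VIII narrative schedule with the Procedure list and the form.

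The cost is wording in Section IX and one schedule sentence in Section VIII, plus slightly more analysis. No new data are needed: baseline, the five scores and rescue are on the form, and dose is on the randomisation list. The downside is the missing-at-random assumption. The changes should be fixed before unblinding. The documents do not show whether that is still possible, since enrolment was planned to end in January 2021 and the protocol is dated 4/20/2021. If it is not, report the model and label it post hoc.

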**Hackensack University Medical Center
Institutional Review Board**

NCT03896230 Unique Protocol ID: Pro2018-0970

Comparison of ketamine 0.1 mg/kg, 0.2 mg/kg, and 0.3 mg/kg intravenous doses for acute pain in the emergency department: A prospective, randomized, double-blind, active-controlled, clinical trial

**[name], BCPS
Emergency Medicine Clinical Pharmacist
Hackensack University Medical Center**

Study Team:

**[name]
[name], BCCCP
[name]**

Version - 4/20/2021

Table of Contents

I.	Objectives of the Study.....	3
II.	Background Material.....	3-5
III.	Drug Information.....	5-6
IV.	Inclusion Criteria.....	6
V.	Exclusion Criteria.....	6
VI.	Recruitment Procedures.....	6
VII.	Definitions.....	7
VIII.	Methodology.....	7-8
IX.	Statistical Considerations.....	8-10
X.	Discomfort and Risks.....	10
XI.	Benefits.....	10
XII.	Criteria for Evaluating Response.....	10
XIII.	Confidentiality.....	10
XIV.	Credentials, Training.....	11
XV.	Bibliography.....	11-13
XVI.	Appendix A.....	14-15
XVII.	Appendix B.....	16-18

I. Objectives of the Study

Primary Objectives

This study will prospectively compare the mean Numerical Rating Scale (NRS) pain score reduction amongst three recommended dosing strategies of intravenous ketamine (0.1 mg/kg, 0.2 mg/kg, and 0.3mg/kg) for acute pain in the emergency department (ED).

Secondary Objectives

This study will also examine the frequency of adverse events secondary to ketamine including fatigue, dizziness, nausea, headache, feeling of unreality, changes in hearing or vision, mood changes, generalized discomfort, and hallucinations, changes in vital signs. Subgroups for exploratory analysis based on the need for rescue analgesia within two hours of ketamine administration, adequate pain relief, previous opioid tolerance, and age (adults < 65 years old and > 65 years old).

II. Background Material

Pain is one of the most common reasons for presentation to the emergency department, with studies reporting it being responsible for up to 78% of visits. Accordingly, pain reduction is one of the primary goals of emergency medicine.¹ Opioids are among the most common analgesics used to treat pain in the emergency department.² The increasing use of opioids has made treating acute pain difficult due to increased concern for opioid tolerance, abuse, and misuse.³

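### The two-group rule names the pooled-variance t-test with only a normality check, so a contrast with unequal group sizes and unequal SDs would miss the nominal 5%

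*Combined protocol and SAP*

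**What the plan says.** Section IX, Exploring Differences, sets two parallel rules for continuous variables.

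- **Two groups:** "The two-sample Student's t-test will be used to compare the continuous variables between groups". The check is on distribution shape only: "The Shapiro-Wilk test will be used to evaluate the normality", and "If the normality assumption is violated, the Wilcoxon rank sum test will be used".
- **More than two groups:** "The one-way analysis of variance (ANOVA) will be used to compare the continuous variables among groups". Here spread is checked as well: "The Bartlett test will be used to evaluate the homogeneity of variances", with the consequence that "If the normality assumption or homogeneity of variances assumption is violated, the Kruskal-Wallis one-way ANOVA by ranks will be used". Tukey or Dunn handles the pairwise follow-up.

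The same section promises 95% confidence intervals and two-sided p values, and adds: "A p value of 0.05 or less will be considered an indication of statistical significance".

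Section I, Secondary Objectives, lists factors for exploratory subgroup analysis: need for rescue analgesia, adequate pain relief, "previous opioid tolerance, and age" (split at 65 years). It gives no subgroup sizes. The only SD in the protocol is a single illustrative 3.4, under Power and Sample Size.

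**The concern.** The plan treats unequal variance as a threat when three groups are compared but gives no action when two are compared. Shapiro-Wilk does not detect a difference in spread, so the one check attached to the t-test cannot catch the problem.

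The 1:1:1 block randomisation balances the dose arms only. Nothing balances opioid-tolerant against non-tolerant patients, or younger against older ones. The definition of opioid tolerance in section VII is demanding, and section V excludes patients on active methadone, so a minority group is a reasonable expectation, though the protocol does not say so.

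The pooled test gives most weight to the variance of the larger group. If the smaller group is more variable, the standard error is too small, p values are too low and intervals too narrow. If the smaller group is less variable, the reverse holds. Since this trial is meant to inform a larger one, a subgroup difference flagged or missed for this reason could misdirect planning.

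**Working it through.** **Inputs.** From the protocol: two-sided alpha of 0.05; 180 patients, 60 per dose; Student's t for two groups, with Wilcoxon if normality fails. Assumed, because the protocol does not give them: splits of 45/135, 36/144 and 18/162, and an SD in the smaller group that is 1.25 or 1.5 times larger or smaller than in the larger group.

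**Formula.** With group sizes n1, n2 and true SDs s1, s2:

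- true variance of the mean difference: V = s1²/n1 + s2²/n2
- variance the pooled test uses, on average: P = [((n1−1)s1² + (n2−1)s2²)/(n1+n2−2)] × (1/n1 + 1/n2)
- k = √(P/V); true error rate ≈ 2 × [1 − Φ(k × 1.973)], where 1.973 is the critical value on 178 degrees of freedom.

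**Baseline.** The plan's own figure is the nominal 5%. If s1 = s2, then k = 1. If n1 = n2 = n, both P and V equal (s1² + s2²)/n, so again k = 1. Simulation agrees: about 5.0% at 45/135 with equal SDs, and 5.0-5.1% at 60/60 with an SD ratio up to 2.

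**Worked case, 36/144, smaller group's SD 1.5 times larger.** V = 2.25/36 + 1/144 = 0.0694. P = [(35 × 2.25 + 143)/178] × (1/36 + 1/144) = 1.246 × 0.0347 = 0.0433. k = √(0.0433/0.0694) = 0.79, so intervals are about 21% too narrow. The effective critical value is 0.79 × 1.973 = 1.56, giving an error rate of about 12%.

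**Same split, smaller group's SD 1.5 times smaller.** V = 0.444/36 + 1/144 = 0.0193. P = [(35 × 0.444 + 143)/178] × 0.0347 = 0.0309. k = 1.27, effective critical value 2.50, error rate about 1.3%.

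**All assumed cases.** Pooled t-test, simulated with normal data and equal means, at least 100,000 trials per cell. The SD ratio is smaller group to larger group.

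| Split | 1.25 | 1.5 | 0.8 | 0.67 |
|---|---|---|---|---|
| 45/135 | 7.9% | 10.7% | 2.9% | 1.8% |
| 36/144 | 8.6% | 12.1% | 2.5% | 1.3% |
| 18/162 | 10.1% | 15.4% | 1.9% | 0.7% |

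Coverage of the pooled 95% interval is 100% minus these figures, for example about 88% at 36/144 with ratio 1.5. Welch's test stays at about 5% (4.8-5.2%) in these settings.

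**Cause.** Small size alone does little: 10/10 with an SD ratio of 2 gives 5.5%, whereas 45/135 with the same ratio, larger SD in the smaller group, gives 15.1%.

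**The full written rule.** NRS scores are whole numbers, so Shapiro-Wilk sends part of the analyses to Wilcoxon. With rounded scores, an overall SD of 3.4 and an SD ratio of 1.5, the complete rule gives about 10% at 36/144 and 13-14% at 18/162 when the smaller group is more variable. When it is less variable, the rate is 1.4-1.7%. A further case, 30/150 at ratio 1.5 with scores also truncated to a plausible range, used Wilcoxon in more than 90% of trials and gave 8.5% and 2.2%. The fallback softens the error but does not restore 5%.

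**The case against.** The strongest reply is that the plan never specifies the comparison at issue. The objective and the null hypothesis concern three doses, and the ordinary reading of a subgroup analysis is a dose comparison within each subgroup. That again falls under ANOVA with Bartlett, and pairwise dose contrasts go to Tukey or Dunn. This largely stands: the protocol does not commit to comparing, say, tolerant with non-tolerant patients across doses. What survives is that the plan states a two-group rule, names two-category factors to which it could apply, and leaves that rule without protection.

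Second, the group sizes and SD ratios are not in the protocol. That stands in full. Nothing there suggests that one subgroup is 1.5 times as variable as the other. With an overall SD of 3.4 and an 18/162 split, that ratio would mean SDs of about 4.8 and 3.2.

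Third, the subgroups are exploratory and each test uses an unadjusted 0.05, so no strict error control is claimed. That limits the harm, but it is no reason to keep the less robust of two equally simple tests.

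Fourth, R, one of the two packages named, runs Welch's test by default, so the gap may be only in the wording. If so, correcting the wording costs nothing.

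**Conclusion.** The point holds as a minor gap in specification. The two-group rule has no provision for unequal variances, and the normality check with its Wilcoxon fallback does not supply one. The size is conditional: about 5% if either the sizes or the SDs are equal, and about 8-15% or about 1-3% under the assumed splits and SD ratios of 1.25 to 1.5, with the direction set by whether the smaller group is more or less variable.

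A reader might infer three stronger things, none of which the protocol supports:

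- That the trial's error rate is 12-15%. Those values need both a marked imbalance and a marked difference in spread, and the protocol gives neither.
- That small subgroups are the problem. The cause is imbalance combined with unequal spread.
- That the main result is at risk. The three-dose primary comparison uses a different rule that does check variances, and full dose arms of 60 are robust in any case.

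**What to change.** In section IX, Exploring Differences, replace the two-sample Student's t-test with Welch's two-sample t-test, and state that the mean difference will be reported with its Welch 95% CI. No variance pre-test is needed. It would also help to list which two-category contrasts, if any, will be run.

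The cost is one change of name, with no new data. If the variances are in fact equal, some power is lost: from 79.5% to 78.6% at 36/144 (about 1 point) and from 79.5% to 76.2% at 18/162 (about 3 points). The loss is small but not nil when the split is extreme.

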patient in each group, we will need to have 157 patients in each group. That is, a total of 471 patients (157 in each group) will be needed.

X. Discomfort and Risks

The risks of this study are minimal, as ketamine is currently the standard of care for acute pain in the Adult Emergency Department at Hackensack University Medical Center.

Side effects associated with ketamine are fatigue, dizziness, nausea, headache, feelings of unreality, changes in hearing, changes in vision, mood changes, generalized discomfort, and hallucinations.

Emergence reactions will be treated per hospital protocol with short active benzodiazepines. Midazolam 1 mg IV once (or 0.5 mg IV in the elderly) administered by the provider is typically sufficient, but doses may be repeated if necessary.

If there is a significant delay from the initial pain score to the study dose of ketamine, the patient will be withdrawn from the study and receive standard of care treatment. If pain is not controlled after the administration of ketamine, providers can order an IV analgesic of their choice as a rescue analgesic.

XI. Benefits

There will be no direct benefits to patients whose data is included in the analysis. The results of this study will help to better determine the ideal dose of intravenous ketamine for acute pain in the emergency department.

XII. Criteria for Evaluating Response

Specific patient information will be obtained from patients using a data collection form (Appendix A) and will include

- Demographics (age, sex, weight)
- Type of pain
- NRS pain rating
- Previous opioid usage
- Need for rescue analgesia
- Vital signs (heart rate, respiratory rate, blood pressure)
- Presence of side effects secondary to ketamine

XIII. Confidentiality

All study related materials will be kept confidential as required by law. Written documentation and computer files will remain in a locked or password protected location, with access given to those directly responsible for the conduct of the study. In addition, all information will be recorded in such a manner that subjects whose data is included in the analysis cannot be identified directly or through identifiers linked to the subjects. A data collection tool can be found at the end of this protocol (Appendix A).

XIV. Credentials, Training

All investigators have completed the Collaborative Institutional Training Initiative.

List of investigators

- [name], BCPS
- [name]
- [name], FACEP
- [name], DO
- [name]
- [name]

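### The primary null is on mean NRS reduction, but pre-tests can move the primary test to ranks, where no adjusted between-dose mean difference is planned; baseline NRS is not used as a covariate

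*Combined protocol and SAP*

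**What the plan says.** All of this is in section IX of the combined protocol and SAP unless another place is named.

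- **Target.** Under Primary Outcome, for the reduction from baseline to 120 minutes: "The null hypothesis is that there is no difference among those three doses with respect to the mean score reduction".
- **Test.** Exploring Differences gives one-way ANOVA with Tukey comparisons for continuous variables among groups, with Shapiro-Wilk and Bartlett as checks. Then: "If the normality assumption or homogeneity of variances assumption is violated, the Kruskal-Wallis one-way ANOVA by ranks will be used". On that path, "The Dunn test will be used to perform the multiple comparisons". The section does not state the level of the pre-tests, whether Shapiro-Wilk is applied by arm or to residuals, or how Dunn p values are adjusted. No separate test is named for the primary outcome, so I take the generic rule to govern it.
- **Description.** "The continuous variables (such as age of participant at the time of study) will be summarized using mean, median, standard deviation" and other summaries, whichever test is used. Also: "The 95% confidence interval on the variables of interest will be calculated".
- **Baseline.** The data collection form in Appendix A records an initial pain score just before randomization. No covariate is named. Under Exploring Associations, "the regression models will be explored if there is any significant difference identified from the results of previously described statistical testing".
- **Planning example.** Power and Sample Size illustrates a later study with an effect "such as a mean difference of 1.25 between consecutive doses with the standard deviation of 3.4", from which "we will need to have 157 patients in each group".

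**The concern.** Kruskal-Wallis and Dunn compare ranks. They speak to means only if the arms differ by a pure shift, and unequal variances, one of the two triggers, contradict that condition. The rule can therefore leave the stated null in a situation where ranks answer it least well. Because the pre-test details are open, two analysts could also take different paths on the same data.

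The trial calls itself exploratory, so its main product is a set of estimated differences between doses. On the ANOVA path Tukey supplies adjusted mean differences. On the rank path nothing named does so, and the general commitment to 95% intervals is tied neither to between-dose differences nor to multiplicity.

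The baseline question is separate. Regression is allowed only after a significant test, so any baseline adjustment would depend on the result. At stake are some precision and some protection against chance imbalance. Bias is not at stake.

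**Working it through.** **1. The plan's own figure.** Inputs from Power and Sample Size: difference 1.25, SD 3.4, power 80%, alpha 0.05. A two-sided two-sample t-test by noncentral t needs 118 per arm at 0.05 and 157 per arm at 0.05/3 (power 0.802). The stated 157 is thus reproduced as a pairwise comparison of means, Bonferroni-adjusted for three pairs. The documents do not state the division by 3; it is inferred from the match.

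**2. What 60 per arm gives on means.**
- Tukey-type 95% half-width for a pairwise difference: q(0.05; 3, 177)/√2 × 3.4 × √(2/60) = 3.343/1.414 × 0.621 = 1.47 points.
- 2-df ANOVA power at equal steps d between consecutive doses has noncentrality 60 × 2d²/3.4². For d = 0.75 and 1.25 this is 5.84 and 16.22, giving power 0.564 and 0.956.

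**3. How often the switch fires, and what it changes.** Simulations at 60 per arm, pre-tests at 0.05 (an assumption):

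| Data | Switch, residuals | Switch, by arm |
|---|---|---|
| Exactly normal, equal variances | 9-10% | 18-19% |
| Whole-number NRS bounded 0-10 (assumed distributions) | 20-92% | 35-96% |

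The planned two-stage procedure and plain ANOVA reached different verdicts in 0-4.4% of trials, and type I error of the planned procedure was 4.0-6.3%. In a separate bounded-NRS run with steps of 1.25, power was 93.8% for ANOVA, 93.6% for Kruskal-Wallis and 93.5% for the two-stage procedure.

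**4. Can ranks reject when means are equal?** Yes, by construction. Let arms 1 and 2 be triangular on -4 to 10 (mean 3, SD 3.24). Let arm 3 take the values 0/1/2/3/9/10 with probabilities .25/.28/.17/.07/.13/.10 (mean 3.00, SD 3.62). In 5,000 trials the switch fired every time, Kruskal-Wallis rejected in 15.1% and ANOVA in 4.7%. The protocol's Definitions section counts a drop of at least 3 points as adequate relief. On that measure the arms have 36/64 = 56%, 56% and .07 + .13 + .10 = 30%, so they truly differ on a protocol outcome.

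**5. Baseline adjustment.** The documents give neither the baseline SD nor its correlation r with the 120-minute score. Assume baseline SD 1.8 and r 0.2-0.5, and hold the change SD at 3.4. Then:
- SDf = 1.8r + √(1.8²r² − 1.8² + 3.4²), the SD of the 120-minute score
- variance ratio (adjusted to unadjusted) = SDf²(1 − r²)/3.4²
- shift in the unadjusted difference from a baseline imbalance at its 95% limit, 1.96 × 1.8 × √(2/60) = 0.64 points: 0.64 × (1 − r·SDf/1.8)

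| r | SDf | Variance ratio | Power, step 0.75 | Power, step 1.25 | Shift (points) |
|---|---|---|---|---|---|
| unadjusted | – | 1 | 0.564 | 0.956 | – |
| 0.2 | 3.27 | 0.886 | 0.619 | 0.974 | 0.41 |
| 0.3 | 3.47 | 0.950 | 0.587 | 0.965 | 0.27 |
| 0.4 | 3.69 | 0.991 | 0.568 | 0.958 | 0.12 |
| 0.5 | 3.92 | 0.998 | 0.565 | 0.956 | -0.06 |

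The adjusted rows allow for the lost degree of freedom (176 instead of 177).

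**The case against.** The case for leaving the plan alone is substantial. The trial is exploratory and the test rule is generic. Dunn does provide pairwise comparisons on the rank path. The switch scarcely affects error rates. Randomization makes the unadjusted change score unbiased. The 157 per arm belongs to a hypothetical later study. All of this stands, and it limits the size of the point. It does not fix which hypothesis the primary p value tests, or supply an adjusted mean difference on the rank path.

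A reader might infer four stronger things that the documents do not support.

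- **That the rank path blocks sizing of the next study.** It does not. Arm means and SDs are reported on either path, a difference is one subtraction, and a multiplicity-adjusted interval is not an input to a sample size.
- **That the switch inflates false positives to about 15%.** That figure belongs to one constructed case in which dose changes the shape of response. Those arms differ on the protocol's own relief outcome, so the rank test is detecting a real difference, though not one in means. It is not an expected error rate.
- **That baseline adjustment could cut the variance by about a third.** A ratio of 0.65 arises if baseline and 120-minute SDs are equal and r = 0.3: (1 + 0.3)/2. With a change SD of 3.4 this needs a baseline SD of 3.4/√(2 × 0.7) = 2.87. Eligible scores run from 4 to 10, so even an even split between the two ends gives an SD of only about 3.0. The ratio should not be relied on.
- **That an amendment now would necessarily be pre-specified.** The current version is dated 4/20/2021, after the stated end of enrolment in January 2021, and the documents do not show the state of blinding.

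**Conclusion.** The point holds as a mismatch between the stated null and the planned test, with a missing estimate on one of the two paths. Its size is mainly interpretive. In the shift scenarios tried, type I error stayed near 5% and power was almost unchanged. Rejection by ranks with equal means requires dose to change the shape of response. The switch frequencies rest on assumed NRS distributions and an assumed pre-test level, but some switching (9-19%) occurs even with exactly normal data.

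The missing baseline covariate is a lost opportunity and not an error. Under the stated assumptions the variance ratio is 0.89-1.00, worth 0.1 to 5.5 percentage points of power at steps of 0.75. The upper end needs a low correlation between baseline and follow-up scores. The change is worth making because it is inexpensive and brings the primary analysis into line with the plan's own null. The application of the generic rule to the primary outcome is inferred from the absence of any other named test.

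**What to change.** For the primary outcome:

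1. Drop the Shapiro-Wilk/Bartlett switch.
2. Pre-specify one linear model of the 120-minute NRS reduction on dose group (three categories), with baseline NRS as covariate and heteroscedasticity-robust (HC3) standard errors.
3. Test the stated null with the 2-df dose-group test.
4. Report the three pairwise adjusted mean differences with multiplicity-adjusted 95% intervals whatever the p value. Single-step max-t on the robust covariance gives simultaneous intervals.
5. Keep unadjusted ANOVA/Tukey and Kruskal-Wallis/Dunn as sensitivity analyses, and state how Dunn p values are adjusted.
6. Record the change in a dated amendment that states truthfully whether it preceded unblinding. If it did not, keep the planned analysis and show the adjusted model beside it, labelled post hoc.

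The cost is SAP wording, an amendment and one degree of freedom, using a score already on the form. In bounded-NRS simulations the model held 2-df type I error at 4.0-7.0% (mean 5.1%, the same as unadjusted ANOVA), so the benefit to claim is a fixed target and usually some precision, with no claim of better error control.
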